#### **16.1.2. TEAEs** Leading to Discontinuation of Study Medication

TEAEs leading to permanent discontinuation of study medication will be identified by using the category of "Drug Withdrawn (Drug Discontinued)" from the eCRF fields "Action Taken in Regard to Study Drug" on the "Adverse Events" eCRF page.

For TEAEs leading to discontinuation of study medication, summaries by SOC and PT will be prepared. A subject data listing for TEAEs leading to discontinuation of study medication will be provided.

#### 16.1.3. SERIOUS ADVERSE EVENTS

Serious adverse events are those events recorded as "Serious" on the Adverse Events page of the eCRF. A summary of serious TEAEs by SOC and PT will be prepared. A subject data listing for all SAEs will be provided.

#### 16.1.4. Adverse Events Leading to Death

TEAEs leading to death are those events which are recorded as "Fatal" on the Adverse Events page of the eCRF. A summary of TEAEs leading to death by SOC and PT will be prepared. A subject data listing for TEAEs leading to death will be provided.

Document:	\\quintiles.net\Enterprise\Apps\sat	sdata\SASb\SAS\Noven\HP-	
	3070\XWA17541\Biostatistics\Doc	umentation\SAP\Final 6\Noven HP-3070-GL-04 S/	AP text Final
	6_18Jan2018.docx		
Author:	[name]	Version Number:	Final 6
		Version Date:	18Jan2018
Template No:	CS_TP_BS016 – Revision 3	Reference: (	S WL BS005

Effective Date: 01May2012

Copyright © 2012 Quintiles Transnational Corp. All rights reserved.

#### 16.1.5. COMMONLY OCCURRING TEAEs

Commonly occurring TEAEs are defined as those which occur in 5% or more of the subjects in any treatment arm. A summary of commonly occurring TEAEs by SOC and PT will be prepared. A subject data listing for commonly occurring TEAEs will be provided.

#### **16.1.6. AEs at Patch Application Site**

Spontaneous complaints of dermal reactions (skin irritation, discomfort) will be recorded as AEs. Spontaneous reports might include but are not limited to the following: initial dermal response and exacerbation of an existing response. AEs at the patch application site will be summarized by PT and severity for the events occurring during the double-blind period. A subject data listing of AEs at the patch application site will be provided.

# **16.2.** DEATHS

If any subjects die during the study, the information will be presented in a subject data listing.

## **16.3. LABORATORY EVALUATIONS**

A central laboratory designated by the Sponsor will be used for all laboratory assessments during the trial. If an immediate result is required, a sample should be sent to both the local and central laboratory.

Laboratory assessments will include standard measures of hematology, clinical chemistry [including prolactin levels], urinalysis, urine drug screen, and some additional tests as per protocol, Section 6.3. Pregnancy testing will be done for women of child-bearing capacity.

The central laboratory will not report prolactin levels to the sites, Sponsor, or other personnel involved in the study conduct until the overall study unblinding at final analysis, because this could potentially result in unblinding the treatment.

Urine drug screens may be done at the Investigator's discretion. If the subject is allowed to leave the hospital during study, an alcohol breathalyzer and urine drug tests must be done when the subject returns.

Summary tables will summarize laboratory data for each scheduled time point based on the visits at which samples were collected. Unscheduled evaluations will be presented in subject listings, but will not be summarized in tables. Unscheduled evaluations will be used in the determination of baseline values.

All available laboratory data will be presented in subject listings.

Presentations will use standard international (SI) Units for all laboratory tests.

Quantitative laboratory measurements reported as "< X", i.e. below the lower limit of quantification, or "> X", i.e. above the upper limit of quantification, will be converted to X for the purpose of quantitative summaries, but will be presented as originally recorded, i.e. as "< X" or "> X" in the subject listings.

Document:	\\quintiles.net\Enterprise\Apps\sas	data\SASb\SAS\Noven\HP-	
	3070\XWA17541\Biostatistics\Docu	umentation\SAP\Final 6\Noven HP-3070-GL-04 S	AP text Final
	6_18Jan2018.docx		
Author:	[name]	Version Number:	Final 6
		Version Date:	18Jan2018
Template No:	CS TP BS016 – Revision 3	Reference:	CS WI BS005

Effective Date: 01May2012

Copyright © 2012 Quintiles Transnational Corp. All rights reserved.

Laboratory findings will be classified as Low, Normal, and High relative to the laboratory. Central laboratories will also provide a classification of Clinically Significant or Not Clinically Significant abnormalities. Hematology and serum chemistry laboratory findings will also be graded according to National Cancer Institute Common Terminology Criteria for Adverse Events (NCI CTCAE) criteria, version 4.03, as applicable.

The following descriptive summaries will be provided for hematology, serum chemistry, and urinalysis data by treatment group:

- Actual and change from baseline by visit for quantitative measurements
- Shift from baseline to the worst on-treatment result for each category of result for categorical measurements. Worst on-treatment result is defined as the worst result occurring after the administration of the first dose of double-blind study medication.
- Number and percentage of subjects with an absolute neutrophil count of <1000 per mm3 by visit
- Number and percentage of subjects who meet the definition of potential Hy's Law cases at any point during the study. Potential Hy's Law cases are determined based on the FDA Guidance for Industry on Drug Induced Liver Industry, July 2009.
  - $\circ~$  Alanine transaminase (ALT) or Aspartate transaminase (AST) >3x upper limit of normal (ULN) and
  - Alkaline phosphatase (ALP) <2x ULN and
  - O Increase in bilirubin ≥2x ULN

Hy's Law evaluation based on the above

- (ALP) ≤2x ULN [for subjects that meet the criteria of ALP≤2, present ALT or AST elevations with ≥3x ULN]
- o AST ≥3x ULN

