# 6.4. RETESTS, UNSCHEDULED VISITS AND EARLY TERMINATION DATA

In general, for by-visit summaries, data recorded at the nominal visit will be included in analysis. Unscheduled measurements will not be included in by-visit summaries, but will contribute to the worst case value where required (e.g., shift tables).

In the case of a retest (same visit number assigned), the latest available measurement for that visit will be used for by-visit summaries.

Subject data listings will present all available data: scheduled, unscheduled, retest, and ET visit data.

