# **16.4. ECG EVALUATIONS**

Twelve-lead ECGs will be recorded at Screening and at each visit during the double-blind treatment period and at the time the subject discontinues the study early. A central ECG service will be utilized for reading all ECGs in order to standardize interpretations for the safety analysis. In addition, ECG results will be evaluated at the investigational site to monitor safety during the trial. The Investigator or designee will note whether or not any abnormal results are of clinical significance.

The following ECG parameters will be reported for this study:

- PR Interval (msec)
- QRS Interval (msec)
- QT Interval (msec)
- QTc Interval (msec)
- QTcF Interval (msec)
- QTcB Interval (msec)
- HR (bpm)
- Overall assessment of ECG (Investigator's judgment):
  - o Normal
  - o Abnormal, Not Clinically Significant (ANCS)

 

 Document:
 \\quintiles.net\Enterprise\Apps\sasdata\SASb\SAS\Noven\HP-3070\XWA17541\Biostatistics\Documentation\SAP\Final 6\Noven HP-3070-GL-04 SAP text Final 6\_18Jan2018.docx

 Author:
 [name]
 Version Number: Version Date:
 Final 6 18Jan2018

 Template No:
 CS\_TP\_BS016 – Revision 3
 Reference:
 CS\_WI\_BS005

Effective Date: 01May2012

Copyright © 2012 Quintiles Transnational Corp. All rights reserved.

o Abnormal, Clinically Significant (ACS)

The following summaries will be provided for ECG data:

- Actual and change from baseline by visit for quantitative measurements
- Number and percentage of subjects with each category of overall assessment (Investigator's judgement) by visit
- Shift from baseline to worst on-treatment category of overall assessment of ECG. Worst on-treatment result is defined as the worst result occurring after the administration of the first dose of double-blind study medication.
- Number and percentage of subjects with markedly abnormal ECG results (see Section 16.4.2) by visit and incidence of markedly abnormal ECG results for study overall (post-Baseline)

A listing of subjects with at least one post-Baseline markedly abnormal ECG result will be presented and will include all available ECG data for such subjects.

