# Table 14.3.3.4 12-Lead ECG Markedly Abnormal Results by Visit Safety Analysis Set

Visit/		HP-3070 18.0 mg	HP-3070 9.0 mg	Placebo
Abnormality	Statistic	(N=XXX)	(N=XXX)	(N=xxx)
Overall Post-baseline	N	XX	xx	XX
Any Marked Abnormality	n (%)	xx (xx.x)	xx (xx.x)	xx (xx.x)
OT Interval				
Result > 450 msec	n (%)	xx (xx.x)	xx (xx.x)	xx (xx.x)
Result > 480 msec	n (%)	xx (xx.x)	xx (xx.x)	xx (xx.x)
Result > 500 msec	n (%)	xx (xx.x)	xx (xx.x)	xx (xx.x)
Change from Baseline >= 30 msec	n (%)	xx (xx.x)	xx (xx.x)	xx (xx.x)
Change from Baseline >= 60 msec	n (%)	xx (xx.x)	xx (xx.x)	xx (xx.x)
QTcB Interval				
Result > 450 msec	n (%)	xx (xx.x)	xx (xx.x)	xx (xx.x)
Result > 480 msec	n (%)	xx (xx.x)	xx (xx.x)	xx (xx.x)
Result > 500 msec	n (%)	xx (xx.x)	xx (xx.x)	xx (xx.x)
CFB >= 30 msec	n (%)	xx (xx.x)	xx (xx.x)	xx (xx.x)
CFB >= 60 msec	n (%)	xx (xx.x)	xx (xx.x)	xx (xx.x)

Note: ECG = Electrocardiogram, QTcB = QT interval corrected by Bazett's formula, QTcF = QT interval corrected by Fridericia's formula, HR = Heart Rate.

Note: Baseline is defined as the last non-missing measurement taken prior to first dose of double-blind study medication.

Note: Percentages are calculated as (n/N) \* 100, where N is the number of subjects with data at the given visit.

Note: Unscheduled visits are not included in this summary.

Noven\HP-3070\XWA17541\Biostatistics\Production\Tables\xxxxx.sas ddmmmyyyy hh:mm

Author:

[name]

Version Number: Version Date: Draft 2 09Jan2017 Page **94** of **144** 

Page 2 of x

Noven Pharmaceuticals, Inc. STATISTICAL ANALYSIS PLAN: PROTOCOL HP-3070-GL-04

Noven Pharmaceuticals, Inc. Protocol HP-3070-GL-04

Visit/		HP-3070 18.0 mg	HP-3070 9.0 mg	Placebo
Abnormality	Statistic	(N=XXX)	(N=XXX)	(N=XXX)
QTcF Interval				
Result > 450 msec	n (%)	xx (xx.x)	xx (xx.x)	xx (xx.x)
Result > 480 msec	n (%)	xx (xx.x)	xx (xx.x)	xx (xx.x)
Result > 500 msec	n (%)	xx (xx.x)	xx (xx.x)	xx (xx.x)
Change from Baseline >= 30 msec	n (%)	xx (xx.x)	xx (xx.x)	xx (xx.x)
Change from Baseline >= 60 msec	n (%)	xx (xx.x)	xx (xx.x)	xx (xx.x)
HR				
>= 100 bpm	n (%)	xx (xx.x)	xx (xx.x)	xx (xx.x)
PR Interval				
>= 210 msec	n (%)	xx (xx.x)	xx (xx.x)	xx (xx.x)
QRS Interval				
>= 120 msec	n (%)	xx (xx.x)	xx (xx.x)	xx (xx.x)
Week 1				

Table 14.3.3.4 12-Lead ECG Markedly Abnormal Results by Visit Safety Analysis Set

#### ...

Note: ECG = Electrocardiogram, QTcB = QT interval corrected by Bazett's formula, QTcF = QT interval corrected by Fridericia's formula, HR = Heart Rate,

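### SAP Section 16.3 and the footnotes of Tables 14.3.3.4 and 14.3.4.3 exclude unscheduled values that Section 6.4 would count, so an abnormality seen only at an unscheduled assessment could go untabulated

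*SAP*

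**What the plan says.** Section 6.4 gives the general rule: "Unscheduled measurements will not be included in by-visit summaries, but will contribute to the worst case value where required (e.g., shift tables"). For a repeat under the same visit number it adds: "In the case of a retest (same visit number assigned), the latest available measurement for that visit will be used for by-visit summaries".

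Section 16.3 then gives a laboratory rule with no such limit: "Unscheduled evaluations will be presented in subject listings, but will not be summarized in tables". It names one exception: "Unscheduled evaluations will be used in the determination of baseline values". The same section defines its shift endpoint without reference to scheduled visits: "Worst on-treatment result is defined as the worst result occurring after the administration of the first dose of double-blind study medication". It also plans a liver count over the whole study: "Number and percentage of subjects who meet the definition of potential Hy's Law cases at any point during the study".

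For ECG, Section 16.4 plans a by-visit count and also the "incidence of markedly abnormal ECG results for study overall (post-Baseline"). Table 14.3.3.4 has an Overall Post-baseline block for this, under the footnote "Unscheduled visits are not included in this summary". Table 14.3.4.3, for vital signs, has the same block and the same footnote.

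**The concern.** Extra tests tend to be taken because of a symptom or a worrying earlier result. Leaving them out of by-visit means is sensible. Leaving them out of a count of subjects who ever crossed a threshold is not, because such a count exists to catch the extreme value whenever it occurs. If the exclusions are programmed as written, a subject whose only severe QTc, blood pressure or liver value came from an unscheduled assessment would be counted as not having had it, in the tables on which the safety conclusions rest. These events are expected to be few, so one subject can change what a row says.

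**Working it through.** No arithmetic applies. The check sets the rules against each output.

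**Step 1. What counts as a worst-case value.** A subject meets a single-threshold criterion at some time after baseline exactly when that subject's worst post-baseline value meets it. The vital-sign criteria that add a change from baseline behave the same way, since each subject's baseline is fixed. An Overall Post-baseline row is therefore a worst-case result in the sense of Section 6.4, even though that section names only shift tables as its example. The Hy's Law count combines several tests, but its own definition covers the whole study.

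**Step 2. Rules side by side, for unscheduled post-dose values.**

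| Output | Section 6.4 and the endpoint definition | Specific section or shell |
|---|---|---|
| Labs by visit (14.3.2.1 to 14.3.2.3, 14.3.2.9) | Out | Out: no conflict |
| Lab shifts, including CTCAE (14.3.2.4 to 14.3.2.8) | In | Out if 16.3 is literal; no exclusion footnote |
| Hy's Law and ranges of interest (14.3.2.10) | In | Out if 16.3 is literal; no exclusion footnote |
| ECG Overall Post-baseline (14.3.3.4) | In | Out by footnote |
| ECG shifts to worst (14.3.3.3, 14.3.3.5) | In | No exclusion footnote |
| Vital signs Overall Post-baseline (14.3.4.3) | In | Out by footnote |

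**Step 3. ECG: does another table recover the value?** Take a subject whose QTcF exceeds 500 msec only at an unscheduled ECG. Table 14.3.3.4 does not count it. Shift Table 14.3.3.5 does, but its footnote reduces the QT criteria to a value >450 msec or a change >=30 msec, so the subject looks the same as one just over 450 msec. The >480, >500 and >=60 msec categories of Section 16.4.2 appear only in Table 14.3.3.4. For those three categories the subject enters no table.

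**Step 4. Vital signs.** There is no shift table. The quantitative and orthostatic tables (14.3.4.1, 14.3.4.2) are by visit and carry the same exclusion. A markedly abnormal value found only at an unscheduled reading enters no table.

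**Step 5. Laboratory data.** If Section 6.4 governs, the shift, CTCAE, Hy's Law and ranges-of-interest tables are complete. If the Section 16.3 sentence governs, as the more specific rule with baseline its only exception, all of them omit unscheduled draws. The haematology and neutrophil shells show on-treatment results at Weeks 3 and 6 only, and serum chemistry follows the haematology layout, so an extra draw between those visits has no other route into a table.

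**Step 6. What is not lost.** A scheduled value that prompts a repeat stays eligible for worst-case rows; the retest rule displaces it in by-visit summaries only. Early-termination values are assigned to the next scheduled visit by Section 6.3 and so are tabulated.

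**The case against.** The best defence concerns the laboratory data. The disputed sentence directly follows one about summarising results at each scheduled time point, so it can be read as covering by-visit tables only. The shells fit that reading: the exclusion footnote is on the by-visit laboratory tables and absent from the shift and liver tables, and Table 14.3.2.10 repeats the any-time definition. This stands as a plausible account of intent. It does not remove the conflict, because the sentence itself carries no such limit.

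For ECG, the shift tables have no exclusion, and Section 16.4 requires a listing of every subject with a markedly abnormal post-baseline result. Both points are right, but neither yields a count above 480 or 500 msec.

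For vital signs, Section 16.5 plans markedly abnormal incidence by visit only, and the overall block appears only in the shell. The contradiction is therefore weaker here: it lies between Section 6.4 and the shell, with no study-overall promise in the text.

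There are further safeguards. All values are listed, a listing covers clinically significant or Grade >=3 laboratory results, and the adverse event listing notes that potential Hy's Law events are to be entered as events of special interest. The issue is under-tabulation, not loss of data.

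**Conclusion.** The SAP contradicts itself on whether unscheduled values enter worst-case and any-time safety tables, and should be corrected. The effect is certain as written for the ECG >480, >500 and >=60 msec overall rows and for the vital-signs overall rows. For laboratory tables it is conditional on Section 16.3 overriding Section 6.4.

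Three stronger readings are tempting, and the SAP does not support them:

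- A reader might infer that the abnormal result which triggered a repeat is dropped. It is not: a scheduled triggering value stays in worst-case rows. What can be lost is the unscheduled value itself, when it is the only or the worse abnormality.
- A reader might infer that Hy's Law cases and CTCAE shifts will be understated. That holds only under one of two available readings of the laboratory rules.
- A reader might try to size the loss from the planned 204 subjects per arm. That is the evaluable number for the efficacy comparison. A bound on an event rate when no events are seen says nothing about how many values were left out.

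How many subjects are affected depends on how many unscheduled assessments were made and what they showed, which the SAP does not report. The conclusion assumes only that programmers follow the sentence and footnotes as worded.

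**What to change.** 1. In Section 16.3, limit the sentence to by-visit summaries. Add that unscheduled post-dose values contribute to worst on-treatment shifts, CTCAE shifts, Hy's Law counts and ranges-of-interest counts, in line with Section 6.4.
2. In Tables 14.3.3.4 and 14.3.4.3, limit the exclusion footnote to the by-visit rows. State that the Overall Post-baseline block uses all post-dose values: scheduled, unscheduled and retest.
3. In the same two tables, give the overall block its own denominator note (subjects with any post-baseline value), since the present footnote defines N by visit.
4. In Section 16.5, mention the overall vital-signs incidence so that text and shell agree.

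The cost is SAP and footnote wording plus a small change to the record selection for the overall rows. No new data are needed, as the values are already collected and listed, and the by-visit summaries do not change.

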## 3. STUDY DESIGN

## **3.1. GENERAL DESCRIPTION**

This is a Phase 3, randomized, double-blind, placebo-controlled, in-patient, safety, and efficacy study to evaluate HP-3070 for the treatment of schizophrenia.

This study will consist of a Screening/placebo Run-in Period of 3 to 14 days, a 6-week double-blind Treatment Period and a 30 day Follow-up Period.

Subjects will be hospitalized at the Screening Visit and will remain hospitalized during the study. The subject may leave the hospital study for necessary personal business. Any subject who leaves the site must have an alcohol breathalyzer and urine drug tests when they return to the site.

After obtaining informed consent, each subject will be assigned a unique subject number. Eligible subjects will be hospitalized for the duration of the study. While undergoing screening procedures and waiting for results of laboratory tests, ECGs, and other assessments, the subject will start treatment with the single-blind placebo patch. The subject must have the single-blind placebo patch applied for a minimum of 3 days prior to being randomized into the double-blind Treatment Period. In addition, current antipsychotic and other prohibited medications will be washed out during the run-in period and must be completed prior to randomization into the double-blind treatment period. Details in regard to wash-out periods for specific drugs are summarized in Protocol Section 5.10.1. Subjects who have a decrease in PANSS total score ≥20% from Screening to Baseline or a PANSS total score <80 at Screening or Baseline will be discontinued from the study and will not enter the double-blind Treatment Period.

Document:	\\quintiles.net\Enterprise\Apps\sasdata\SASb\SAS\Noven\HP-			
Documenti	3070\XWA17541\Biostatistics\Docu	imentation\SAP\Final 6\Noven HP-3070-GL-04 S/	AP text Final	
	6_18Jan2018.docx			
Author:	[name]	Version Number:	Final 6	
		Version Date:	18Jan2018	
Template No:	CS TP BS016 – Revision 3	Reference: C	CS WI BS005	

Effective Date: 01May2012

Copyright © 2012 Quintiles Transnational Corp. All rights reserved.

Noven Pharmaceuticals, Inc. STATISTICAL ANALYSIS PLAN: PROTOCOL HP-3070-GL-04 Page 12 of 50

Subjects eligible for randomization into the double-blind Treatment Period will be randomly assigned to HP-3070 9.0 mg, HP-3070 18.0 mg, or placebo in a 1:1:1 ratio stratified by country. Subjects will receive treatment with study medication daily for 6 weeks.

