## 8. OUTPUT PRESENTATIONS

Descriptive summaries and statistical analyses will be provided for assessments performed during the doubleblind treatment period and follow-up period. In general, data collected during the screening and single-blind placebo run-in periods will be presented in subject listings only, with the exception of calculated Baseline values which will be summarized and used in analyses as appropriate.

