#### Table 14.3.2.10 Clinical Laboratory Liver Function Abnormalities Safety Analysis Set

	HP-3070 18.0 mg	HP-3070 9.0 mg	Placebo
	(N=XXX)	(N=xxx)	(N=XXX)
Abnormality	n (%)	n (%)	n (%)
ALT > 3xULN	xx (xx.x)	xx (xx.x)	xx (xx.x)
AST > 3xULN	xx (xx.x)	xx (xx.x)	xx (xx.x)
ALP < 2xULN	xx (xx.x)	xx (xx.x)	xx (xx.x)
Potential Hy's Law Cases	xx (xx.x)	xx (xx.x)	xx (xx.x)
ALP <= 2xULN	xx (xx.x)	xx (xx.x)	xx (xx.x)
ALT >= 3xULN	xx (xx.x)	xx (xx.x)	xx (xx.x)
AST >= 3xULN	xx (xx.x)	xx (xx.x)	xx (xx.x)
Other Tests			
Creatine Kinase >= 3xULN	xx (xx.x)	xx (xx.x)	xx (xx.x)
Prolactin >= 4xULN	xx (xx.x)	xx (xx.x)	xx (xx.x)
Total Bilirubin >= 2xULN	xx (xx.x)	xx (xx.x)	xx (xx.x)

Note: ALT = Alanine Transaminase, AST = Aspartate Transaminase, ALP = Alkaline Phosphatase, ULN = Upper Limit of Normal.

Note: Potential Hy's Law Cases are defined as subjects who at any point during the study meet the criteria of ALT or AST > 3xULN, ALP < 2xULN, and Total Bilirubin >= 2xULN.

Note: Percentages are calculated as (n/N) \* 100.

Note: Values for ALT >=3xULN and AST >=3xULN are only presented for subjects that meet the criteria of ALP<=2xULN.

Noven\HP-3070\XWA17541\Biostatistics\Production\Tables\xxxxx.sas ddmmmyyyy hh:mm

Author:

[name]

Version Number: Version Date: Draft 2 09Jan2017 Page 90 of 144 Noven Pharmaceuticals Version No. 1.0 Protocol No. HP-3070-GL-04 14 September 2018

Page 1 of x

Noven Pharmaceuticals, Inc. STATISTICAL ANALYSIS PLAN: PROTOCOL HP-3070-GL-04

Noven Pharmaceuticals, Inc. Protocol HP-3070-GL-04

			HP-3070 18.0 mg	HP-3070 9.0 mg	Placebo
Parameter (Unit)	Visit	Statistic	(N=XXX)	(N=xxx)	(N=XXX)
PR Interval (msec)					
	Baseline	n	XX	хх	XX
		Mean	XX.X	XX.X	XX.X
		SD	XX.XX	XX.XX	XX.XX
		Median	XX	хх	XX
		Min	XX	ХХ	XX
		Max	XX	хх	XX
	Week 1	n	XX	XX	XX
		Mean	XX.X	XX.X	XX.X
		SD	XX.XX	XX.XX	XX.XX
		Median	XX	ХХ	XX
		Min	XX	XX	XX
		Max	XX	XX	XX
	Change from Baseline to Week	n	XX	XX	XX
	1				
		Mean	XX.X	XX.X	XX.X
		SD	XX.XX	XX.XX	XX.XX
		Median	XX	хх	XX
		Min	XX	хх	XX
		Max	XX	XX	XX
		Median Min Max	xx xx xx	xx xx xx	xx xx xx

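### Potential Hy's Law cases are counted over the whole study and the other rows of Table 14.3.2.10 have no time window, so pre-dose values could be booked as events on the randomised arm

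*SAP*

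**What the plan says.** Section 16.3 lists, among the laboratory summaries by treatment group, the "Number and percentage of subjects who meet the definition of potential Hy's Law cases at any point during the study". The footnote of Table 14.3.2.10 uses the same window: "Potential Hy's Law Cases are defined as subjects who at any point during the study meet the criteria of ALT or AST > 3xULN", together with the ALP and bilirubin conditions.

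The table's remaining rows are bare thresholds, for example "Prolactin >= 4xULN". They have no visit, no time window and no Baseline row. In Section 16.3 the creatine kinase, prolactin and bilirubin limits follow the Hy's Law bullet as ranges of interest, also without a window.

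Section 3.1 makes the pre-dose phase part of the study: "This study will consist of a Screening/placebo Run-in Period of 3 to 14 days", followed by the 6-week double-blind period and follow-up. It also says that antipsychotics and other prohibited drugs are washed out during the run-in.

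Section 8 gives the general rule. Summaries cover the double-blind and follow-up periods, and "In general, data collected during the screening and single-blind placebo run-in periods will be presented in subject listings only", with calculated Baseline values excepted.

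**The concern.** A laboratory threshold count by arm should reflect what happened after randomised treatment began. A value above the limit at screening, in the run-in or at Baseline cannot come from the double-blind patch. In this trial it may reflect the antipsychotic being washed out, and prolactin is an obvious candidate. Section 16.3 itself withholds prolactin results from sites and sponsor because they could unblind.

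If such values count, each arm gains a similar number of events unrelated to its treatment, and the ratio between drug and placebo moves towards 1. No formal safety tests are planned (Section 16), so readers will judge from these descriptive counts and percentages.

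A second, smaller point is that the thresholds disagree inside one table. ALP appears as below 2 times and as at or below 2 times the upper limit of normal (ULN). ALT and AST appear as above 3 times and as at or above 3 times ULN.

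**Working it through.** **1. The window, set against the neighbouring rules in the SAP**

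| Item | Window stated |
|---|---|
| Hy's Law count, 16.3 and Table 14.3.2.10 footnote | any point in the study |
| Other rows of Table 14.3.2.10 | none |
| Laboratory shift summaries, 16.3 | after the first double-blind dose |
| Listing of clinically significant or Grade 3 and above results, 16.3 | post-baseline |
| Neutrophil count, Table 14.3.2.9 | by visit, with Baseline as its own row |
| ECG and vital-sign abnormalities, Tables 14.3.3.4 and 14.3.4.3 | overall post-baseline |
| General rule, Section 8 | double-blind and follow-up; run-in data in listings *in general*; Baseline values excepted |

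Table 14.3.2.10 is the exception among these. Pre-dose values will also exist for its subjects. Section 6.2 defines Baseline as the last value up to the first double-blind dose, and the serum chemistry shell follows one that has a Baseline row.

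**2. Does Section 8 settle it?** Not fully. It is qualified as general, it excepts Baseline values, and the Hy's Law wording is specific, written twice, and points the other way.

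**3. Size if pre-dose values are counted**

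The SAP states no laboratory threshold rates, so there is no planned figure to reproduce and every rate below is an assumption.

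Let p be the post-dose rate in an arm and q the pre-dose rate, equal across arms by randomisation and taken as independent of p.

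- Rate at any point = 1 − (1 − q)(1 − p)
- Risk difference at any point = (1 − q) × post-dose risk difference

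With p = 4% on drug and 1% on placebo, the post-dose ratio is 4.0 and the difference 3.0 points.

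| q | Drug | Placebo | Ratio | Difference (points) |
|---|---|---|---|---|
| 5% | 1 − 0.95 × 0.96 = 8.8% | 1 − 0.95 × 0.99 = 5.95% | 1.48 | 2.85 |
| 10% | 1 − 0.90 × 0.96 = 13.6% | 1 − 0.90 × 0.99 = 10.9% | 1.25 | 2.7 |
| 20% | 1 − 0.80 × 0.96 = 23.2% | 1 − 0.80 × 0.99 = 20.8% | 1.12 | 2.4 |

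A second assumed case uses lower pre-dose rates, with post-dose rates of 5% on drug and 1% on placebo (ratio 5.0, difference 4.0 points):

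- q = 1%: 5.95% v 1.99%, ratio 2.99, difference 3.96 points
- q = 5%: 9.75% v 5.95%, ratio 1.64, difference 3.80 points
- q = 10%: 14.5% v 10.9%, ratio 1.33, difference 3.60 points

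With q = 0 nothing changes. The ratio is sensitive even to a small q, whereas the difference loses only the fraction q of itself.

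**The case against.** The strongest reply is that Section 8 already keeps run-in data out of summary tables, and that the whole-study phrase is attached only to the Hy's Law count. On that view the default governs the single-analyte rows, and the Baseline exception is meant for baseline summaries and covariates, not for counting events. Much of this stands. A reader might infer that the SAP definitely counts pre-dose values, but the documents do not go that far. They show a conflict for the Hy's Law count and silence for the other rows. Silence is still a poor instruction when the sibling tables state their limit and the creatine kinase, prolactin and bilirubin limits appear to sit under the same bullet.

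It is also fair to say that post-dose laboratory harm is counted elsewhere. The Low/Normal/High and CTCAE-grade shift tables are limited to results after the first double-blind dose. A reader might take Table 14.3.2.10 to be the plan's only threshold count, and it is not. It is where these particular limits and the Hy's Law cases are counted.

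Two further inferences are tempting and not supported.

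- **Criteria met on different dates.** One could read the phrase as letting the ALT/AST, ALP and bilirubin conditions be met on separate dates, so that the ALP condition would exclude almost nobody. The conditions are joined by *and*, and the natural reading is that the whole definition is met at some point. A same-sample rule would be a preference.
- **The ALP rows as mistakes.** The row at or below 2 times ULN is the conditioning group for the ALT and AST rows beneath it, as Section 16.3 and the footnote explain. Replacing it would remove that context.

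**Conclusion.** The point holds as a conflict over the counting window. Section 16.3 and the Table 14.3.2.10 footnote, taken literally, admit screening, run-in and Baseline values. Section 8 points the other way without settling it, and the neighbouring summaries state a limit that this table lacks. Pre-dose exceedances could therefore be counted as events on the randomised arm.

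The size rests wholly on assumed rates. With 5% to 20% of each arm above a limit before dosing, a true ratio of 4.0 would show as 1.48 to 1.12. A reader might conclude that a drug effect would be hidden. On the difference scale it would not be, since 3.0 points would become 2.85 to 2.4. Pre-dose values meeting all three Hy's Law criteria are probably very rare, so the practical exposure lies in single-analyte rows such as prolactin and creatine kinase. Eligibility rules outside this SAP may make q small for some analytes.

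The mismatched boundaries within the table are a separate, minor inconsistency, independent of any assumption. None of this affects the efficacy analyses.

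**What to change.** - In Section 16.3 and the Table 14.3.2.10 footnote, replace the whole-study window with one that starts after the first double-blind dose, as the shift summaries in the same section already do. State that it applies to every row of the table.
- Show Baseline exceedances in a separate row for each limit, as Table 14.3.2.9 does for neutrophils.
- Reconcile the boundaries so that each analyte has one: ALP below v at or below 2 times ULN, and ALT/AST above v at or above 3 times ULN.

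The cost is a few lines of SAP and shell text, one date filter and an added row in the program. No new data are needed.
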